Date: 10/18/2020 NCT04129216

*THE EFFECTS OF SHORT-TERM
PREOPERATIVE TREATMENT WITH
HORMONAL THERAPY ON GENE PROFILES
IN
BREAST CANCER*

JHM IRB - eForm A – Protocol

- Use the section headings to write the JHM IRB eForm A, inserting the appropriate material in each. If a section is not applicable, leave heading in and insert N/A.
- When submitting JHM IRB eForm A (new or revised), enter the date submitted to the field at the top of JHM IRB eForm A.

1. Abstract

- Provide no more than a one page research abstract briefly stating the problem, the research hypothesis, and the importance of the research.

Breast cancer is among the most common malignancies in women in the United States. Over the years breast cancer management have dramatically developed from the extensive surgical approach toward the breast conservative approach. This was mainly due to the introduction of chemotherapy and hormonal therapy. Hormonal therapy in particular has been shown to improve the oncological outcomes of the breast cancer. However, while this is well documented in the clinical outcomes. Little is known in regards what happens on the genetic level. As such in this study we would like to study the genetic, molecular and functional outcomes that results after a short term neoadjuvant hormonal therapy on patients with breast cancer.

The hypothesize of this study is that short-term, preoperative hormonal treatment will induce genetic changes associated with reduced proliferation, including lower Ki67 expression, and changes in ER and PR expression as well as reduced ER pathway activity. The data from such investigation will be very helpful in advancing the individualized care to women with breast cancer.

Hypothesis

- We hypothesize that short-term, preoperative hormonal treatment will induce genetic changes associated with reduced proliferation, including lower Ki67 expression, and changes in ER and PR expression. as well as changes in ER pathway activity measures

2. Objectives

The purpose of this study is to evaluate the effects of short-term preoperative treatment with hormonal therapy (tamoxifen, letrozole, and exemestane, administered according to standard of care) on gene expression profiles in patients with breast cancer. As such:

- A. Primary objective is to determine whether there is a reduction in the expression of proliferation marker Ki67, measured by IHC as well as single-gene read out, following short-term preoperative treatment with hormonal therapy.

Secondary objectives are to determine whether short term treatment results in significant reductions in the Mammaprint risk score, or in ER or PR expression as measured by IHC and single-gene read out or a change in ER pathway activity. **C. Exploratory objectives:**

- a. Identify differentially expressed transcripts after short-term pre-operative, hormone treatment
- b. Identify transcripts for which gene expression is associate with measures of response, including changes in Ki67, ER and PR.
- c. Perform full-transcriptome set analysis to identify pathway level changes associated with treatment.
- d. Comparison of expression changes between two standard of care molecular diagnostics: 70-GS and 21-GA
- e. Perform OncoSignal pathway activity analysis on pre and post treatment samples to related pathway activity to patient response

The participants of this study will be clinical breast cancer patients of the Principal Investigator (PI) or those referred by community physicians to the PI. The breast cancer patients will be evaluated by the PI or a study team member to assess if they meet inclusion/ exclusion criteria for this study. If the patient meets all the criteria, the consent process will take place.

Participants will include 30 breast cancer patients. These patients will be recruited from Johns Hopkins University cancer treatment centers.

This is a clinical trial with three treatment groups including tamoxifen, letrozole, and exemestane. Ten pre-menopausal patients and men will be in their own group and will receive tamoxifen. Twenty post-menopausal patients will in a separate group and will receive letrozole or exemestane. Treatment selection will be at the discretion of the medical oncologist. Ten patients will be allocated to each treatment group, for a total of 30 patients.

Genomic data will be collected as a part of the standard of care 70 gene signature (70GS; trade name MammaPrint), which is read from the comprehensive-genome microarray at Agendia (Irvine, CA). The 70GS will be performed on the baseline biopsy specimen as SOC, and experimentally on the surgical specimen collected after short-course endocrine treatment. We will then compare the genomic profiling between the two samples to measure changes in gene expression before and after treatment. Special care will be taken to verify with pathology that the baseline biopsy is large enough to run the commercially available 21 gene assay (21GA; trade name Oncotype) on, as this assay is also currently considered standard of care. For the OncoSignal test about 0.25mm³ FFPE tissue is needed from the same biopsy or surgical material. The tumor content should be at least 50%. If on a slide of 5 μm thickness about 25-50 mm² tissue is available, only 2 slides are required.

3. Background

Breast cancer is the most common malignancy and the second leading cause of cancer deaths among women [1]. As a heterogeneous and phenotypically diverse disease, breast cancer may necessitate divergent treatment strategies, among which cytotoxic chemotherapy remains an integral part of therapy at any given stage. However, cytotoxic therapy is not considered a “targeted therapy”, because it does not act on cellular pathways involved in cell growth and progression [1]. The real targeted therapy would be based on the identification of a molecular growth pathway and on the modification of its activity in order to block the growth and progression of cancer. With regard to breast cancer, the endocrine manipulation is considered as a targeted therapy [2]. The role of estrogen on tumor cell growth is well established in breast cancer. Identification of the estrogen receptors (ER) provided the first target for anti-estrogenic therapeutic agents [1-3]. Tamoxifen, the prototype SERM (Selective Estrogen Receptor Modulator), has been the gold standard treatment for early and advanced disease and its activity on ER is considered the first form of molecular targeted therapy [1, 4]. Aromatase inhibitors (e.g., anastrozole, letrozole, or exemestane) which directly inhibit the production of estrogen, have shown superiority over tamoxifen in adjuvant and metastatic setting [5-8], also they appear to fare better than tamoxifen in the neoadjuvant setting [8], where therapeutic agents are administered before the main treatment (e.g. in the preoperative phase). Following the success of adjuvant endocrine treatments [9-11], more studies have been emerging with the use of endocrine agents in the neoadjuvant setting (PO24 trial [12], IMPACT trial [13] and PROACT trial [14]). The objective of endocrine therapy in the neoadjuvant setting is primarily to produce sufficient response in the tumor to allow mastectomy in inoperable tumors and potentially breast conservation in patients initially proposed to undergo mastectomy [8]. Treatment response to these “targeted therapies” differs vastly across different populations; even patients with the same stages of disease can have markedly different responses and overall outcome [10]. Therefore, an ideal therapy should be tailored based on individual characteristics so that each patient receives a treatment with an appropriate response and the least adverse effects. Genetic breakthroughs in the last few decades have provided us with a unique opportunity to address this challenge. The emergence of genomic techniques (e.g. complementary DNA microarrays) and their ability to simultaneously measure the expression of thousands of genes have led to the identification of biology-based prognostic profiles [15-18], several of which have been validated and are in clinical use. The development of prognostic profiles has been particularly useful in guiding decision-making about adjuvant therapy along with well-established clinical prognostic factors (e.g. patient age, comorbidity, tumor size, grade, and nodal status) [19]. These molecular prognostic profiles can augment but do not replace classic clinical factors. They offer the potential for use in clinical practice for prognostic stratification and treatment selection for patients with breast cancer, particularly if they are hormone receptor-positive. Among the available prognostic profiles, the Amsterdam 70-gene prognostic profile (Mammaprint) was one of the first gene expression array-based marketed for prognostic purposes [20]. The test was developed using a supervised DNA microarray analysis of gene expression arrays on frozen tissue from primary breast tumors. A mathematical model is used to calculate a score that stratifies patients as having a breast cancer with an associated poor-prognosis (High risk: 29% risk of metastasis after 10 years, without adjuvant treatment) or good-prognosis (Low risk: 10% risk of metastasis after 10 years without adjuvant treatment) [21]. Validation of the Mammaprint gene expression profile demonstrated that the profile is a powerful prognostic factor to predict outcome in lymph node-negative and lymph node-positive breast cancer. Recent reports, that the most important of them is MINDACT trial [22, 23], confirm this predictive value for Mammaprint signature. Although it was originally approved for use with unfixed, frozen tissue, it has now been adapted for use with formalin-fixed, paraffin-embedded tissue. Neoadjuvant endocrine therapy has been increasingly employed in clinical practice to improve the disease outcome [6-8], but little is known of the molecular effects of these agents. Particularly, the genetic impact of endocrine therapy directly on breast cancer remains largely unexplored. Most studies that examined the anti-estrogen treatment of ER positive breast cancer, have measured changes in clinical, pathological, proliferative or surgical outcomes [7, 25, 26] and

one study investigated the effect of neoadjuvant treatment on ER pathway activity (34; Inda et al; Mol Can Ther 2020 19 680-9) To our knowledge, there are few studies that have shown molecular effects as the early (10-14 days) or late (3-4 months) changes in gene profile after preoperative anti-estrogen treatment of ER-positive breast cancer [26, 27]. Most reports of the transcriptional profiling of estrogen responses in breast cancer cell lines are results of in vitro [28-31] or animal models [32]. Thus, identification of in vivo responses needs to be more elaborated. On the other hand, these studies generally examined one type of neoadjuvant therapy, therefore a comparative study on this subject can be very useful. Preoperative endocrine therapy in neoadjuvant settings revealed to be ideal for this purpose because it allows the direct assessment of response to treatment, and tumor is readily available for multiple time point biopsies [7].

The FLEX Registry (NCT03053193) is a large-scale, population based, prospective registry. All patients with stage I to III breast cancer who receive MammaPrint testing on a primary breast tumor are eligible for entry into the FLEX Registry, which is intended to enable additional substudies at low incremental cost. This study will utilize FLEX's adaptive study infrastructure to capture clinical data.

4. Study Procedures

- a. Study design, including the sequence and timing of study procedures (distinguish research procedures from those that are part of routine care).

The breast cancer patients will be evaluated by the PI or a study team member to assess if they meet inclusion/ exclusion criteria for this study. If the patient meets all the criteria, the consent process will take place. This protocol is designed to be a companion substudy of FLEX Registry, which prospectively observes patients receiving MammaPrint as a part of their care, and data collection will occur within FLEX's eCRF infrastructure. All patients consenting to screening for this study will be co-enrolled in FLEX, with appropriate dual informed consents obtained to participate in both studies.

Participants will include 30 breast cancer patients. These patients will be recruited from Johns Hopkins University cancer treatment centers.

This is a clinical trial with three treatment groups including tamoxifen, letrozole, and exemestane. Ten pre-menopausal patients and men will be in their own group and will receive tamoxifen. Twenty post-menopausal patients will in a separate group and will receive either letrozole or exemestane. Treatment selection will be at the discretion of the medical oncologist. Ten patients will be allocated to each treatment group, for a total of 30 patients. Full genome Mammprint will be run on the biopsy specimen and the final surgical specimen. We will then compare the gene profiling between the two results. OncoSignal pathway analysis will make use of the same biopsy specimen for evaluating the ER pathway activity scores.

The Oncosignal results will not be shared with patients(subjects), treating physicians; nor will be used for patients' management; It only will be used for research purposes.

In addition, some clinical data will be collected from the patient's medical records, operative/pathology reports, and clinical notes. This information will include information such as details of the cancer diagnosis, details of the surgery and further treatment of the disease.

Study design is illustrated in Figure 1.

Figure 1. Study Scheme

[figure not shown]

Figure 1. Study Scheme

Assays and Tests used in the study:

Mammaprint: This is a strong diagnostic tool that will be used in the study as Breast Cancer Assay and will provide invaluable information regarding the genomics of the patient and their tissue sample. We will be running the test twice to ascertain the differences between the samples due to a short term hormonal therapy course.

- OncoSignal: This is a test that measures biologically active pathway activities of 4 different pathways (ER, AR, PI3K and MAPK). In this study especially the ER-pathway activity is

relevant since ER staining positive tumors are selected with an intend for hormonal treatment. From previous studies it is known that, although tumors can be ER positive in staining, the pathway is not always equally active (34). High ER pathway activity on the primary biopsy leads to a better response to hormonal therapy as compared to samples with a low ER activity on the primary biopsy, although all are ER staining positive. Also the change in pathway activity is higher in patients that respond to hormonal therapy as compared to patients that do not, or suboptimally respond, to hormonal treatment. The test requires 0.25mm³ FFPE tissue with a tumor percentage of at least 50%. In principle the same biopsy material can be used as collected for mammaprint but the processing of the FFPE samples is different

Study Drug Information(Dosage, Administration Frequency, Duration):

Tamoxifen: 20mg is administered daily. Patients take this drug for 2-6 weeks.

Letrozole: 2.5mg is administered daily. Patients take this drug for 2-6 weeks

Exemestane: 25mg is administered daily. Patients take this drug for 2-6 weeks.

b. Study duration and number of study visits required of research participants.

We anticipate this study to be done in 2 years. Following consent, and prescription of hormonal therapy, patients will have only one study visit prior to surgery, to take a baseline core research biopsy. The surgical sample will be used for post-treatment analysis

c. Blinding, including justification for blinding or not blinding the trial, if applicable.

d.

This is a single arm trial and so will not be blinded.

e. Justification of why participants will not receive routine care or will have current therapy stopped.

Participants will receive routine care. Normally, patients are scheduled for surgery after radiologic and other workups are completed. After surgery, they will receive hormonal therapy. In our study, hormonal therapy will commence after patients are recruited to the study and informed consent is signed, prior to surgery. Hormone therapy will continue after surgery.

f. Justification for inclusion of a placebo or non-treatment group.

There is no placebo or non-treatment group.

g. Definition of treatment failure or participant removal criteria.

Treatment failure happens if the patient doesn't comply with the hormonal therapy treatment plan. At such cases, the patient will be removed from the study. If any patient miss more than two doses of the medication they will be removed from the study.

Because the duration of the study is short, and the medications are well tolerated, we expect very few non-compliant patients. We will add additional patients to the study if we lose any due to this clause.

- h. Description of what happens to participants receiving therapy when study ends or if a participant's participation in the study ends prematurely.

This is expected to be a rare event as patients are only followed for 2-6 weeks, until surgery, and the hormonal therapy administered in this study is well studied and carries minimal risk of long term effects or consequences. In such cases, patients will continue their standard of care plan as advised by their care providers.

5. Inclusion/Exclusion Criteria

A. Inclusion criteria:

- Treatment-naïve, histologically confirmed invasive ductal breast cancer between stages 1 to 3.
- Co-enrollment in the FLEX Registry
- ER+ PR+ confirmed hormone receptor status measured by immunohistochemistry(IHC)
- Patients should understand their condition and be able to give informed consent to participate

B. Exclusion Criteria:

- History of hormonal therapy, chemotherapy, radiation therapy, or novel therapy to treat the current breast cancer.
- Allergic reactions/hypersensitivity to tamoxifen, letrozole, or exemestane or any of their ingredients.
- Any contraindication to hormonal therapy, such as history of thromboembolic disease or uterine cancer.
- Patients without invasive disease (stage 0)
- Patients with metastatic breast cancer(stageIV)
- Patients that are HER2+ by IHC/FISH.

Drugs/ Substances/ Devices

a. The rationale for choosing the drug and dose or for choosing the device to be used.

The drugs in this study are FDA approved medications and drugs of choice for hormone therapy according to NCCN (National Comprehensive Cancer Network) guidelines. We will use the standard recommended daily doses of the drugs.

MammaPrint has 510k FDA clearance as a device and is a cost-effective vehicle for evaluating the genomic objectives of this study. The patient population considered for enrollment in this trial are candidates for receiving MammaPrint as a part of their standard of care.

The rationale for using the Oncosignal in addition to Mammaprint is that Oncosignal shows differences in pre treatment ER pathway activity scores between patients, although all patients are ER staining positive this does not always relate to an active pathway. Mammaprint test can

show the gene level changes and oncosignal can show the whole pathway activity before and after treatment

- b. Justification and safety information if FDA approved drugs will be administered for non-FDA approved indications or if doses or routes of administration or participant populations are changed.**

The drugs that will be used are FDA approved to be administered for an FDA approved indication.

- c. Justification and safety information if non-FDA approved drugs without an IND will be administered.**

No non-FDA approved drugs without an IND will be administered

Study Statistics

- a. Primary outcome variable:** The primary outcome variable is Ki67 expression, a measure of tumor proliferation
- a. Secondary outcome variables:** Secondary outcomes include ER and PR expression and pathway activity patterns pre and post treatment
- b.**
- c. Statistical plan including sample size justification and interim data analysis.**

Primary Objective: Change in Ki67 expression after treatment will be calculated by subtracting %Ki67 expression at time of surgery from the baseline level. We will then fit a linear model to determine whether short-term treatment significantly reduces expression, while adjusting for choice of treatment, ER and PR level, and other possible cofounders. In a secondary analysis, we will evaluate individual treatment groups separately.

Sample size justification: Power calculations are based on the use of a one-sided, one-sample t-test to evaluate a decrease in Ki67. The proposed sample size of 30 subjects offers at least 90% power at an alpha of 0.05, to detect a decrease greater than 0.55s.d. For the analysis of individual treatment groups of 10 offer at least 90% power to detect decreases greater than 1s.d.

Secondary objectives

Determine whether short term treatment results in significant reductions in Mammaprint risk score, ER or PR expression as measured by IHC.

Change in risk score ER and PR expression will be evaluated as described above for Ki67, using linear regression to model the change in each variable while adjusting for ki67 in addition to the covariates described above. Expected power is the same as for the primary analysis.

Exploratory analyses

Identify differentially expressed transcripts after short-term pre-operative, hormone treatment

Identify transcripts for which gene expression is associate with measures of response, including changes in Ki67, ER and PR expression.

We will fit empirical Bayes linear models [32] to identify genes for which expression is associated with response to treatment, controlling type I error at an FDR of <10%. Wilcoxon Rank Sum tests will be used to perform Gene set enrichment analysis on the results to identify pathways that are significantly altered after short-term treatment. [33]

Show differences in pre treatment ER pathway activity scores between patients, although all patients are ER staining positive this does not always relate to an active pathway. Show differences in ER pathway activity scores between pre and post treatment samples, indicating a measurable biological effect of the treatment.

d. Early stopping rules.

There are no early stopping rules.

6. Risks

a. Medical risks, listing all procedures, their major and minor risks and expected frequency.

Important drug adverse effects like increased risk of thromboembolism would be considered a major risk. The other non-specific side effects may be considered as minor risk. Since the drugs are administered over a short period, it is highly unlikely to develop an adverse event that requires chronic use of the drug.

The Oncosignal test has minimal risks:

It is noninvasive, does not require an invasive sampling that presents significant risk, does not introduce energy into a subject and is not used as a diagnostic procedure without confirmation of the diagnosis by another medically established diagnostic product or test

The Oncosignal results will not be shared with patients(subjects), treating physicians; nor will be used for patients' management; It only will be used for research purposes.

b. Steps taken to minimize the risks.

Known adverse effects of tamoxifen and anastrozole will be recorded using a checklist every week by the research assistant. Medical monitoring will be made by both the principle investigator and the Institutional Data and Safety Monitoring Board. Patients are informed about all common and important adverse effects and they are advised to report as soon as they notice them. They are also advised to take some preventive measures for example for the prevention of

deep vein thrombosis. In any circumstances, all adverse effects are taken care of by the research team immediately and effectively.

Participants are provided with the investigators contact information and a list of frequently asked questions for any concerns they might have.

c. Plan for reporting unanticipated problems or study deviations.

Any unanticipated problem or study deviation will be recorded and reported per IRB guidelines.

d. Legal risks such as the risks that would be associated with breach of confidentiality.

There is a minimal risk of losing confidential data. However, all measures advised by IRB to minimize this risk will be done. Best practices will be followed, including the assignment of a study ID and the de-identification of PHI from study data.

e. Financial risks to the participants.

N/A

7. Benefits

a. Description of the probable benefits for the participant and for society.

You will not directly benefit from being in this study. If you take part in this study, you may help others in the future.

8. Payment and Remuneration

a. Detail compensation for participants including possible total compensation, proposed bonus, and any proposed reductions or penalties for not completing the protocol.

Participants will not receive compensation.

9. Costs

a. Detail costs of study procedure(s) or drug (s) or substance(s) to participants and identify who will pay for them.

Costs of the study will be paid for using the grant funding this study.

References:

4. Coates AS, Keshaviah A, Thurlimann B, Mouridsen H, Mauriac L, Forbes JF, et al. Five years of letrozole compared with tamoxifen as initial adjuvant therapy for postmenopausal women with

endocrine-responsive early breast cancer: update of study BIG 1-98. *Journal of clinical oncology : official journal of the American Society of Clinical Oncology*. 2007;25(5):486-92. Epub 2007/01/04.

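### The primary Ki67 test is an adjusted linear model with no stated contrast and an open covariate list, while the alpha and 90% power belong to an unadjusted one-sample t-test

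*Combined protocol and SAP*

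**What the plan says.** All the analysis text is in the Study Statistics section, item c. Under Primary Objective, the outcome is baseline %Ki67 minus %Ki67 at surgery, so a positive value is a decrease. The analysis is to "fit a linear model to determine whether short-term treatment significantly reduces expression, while adjusting for choice of treatment, ER and PR level". The adjustment set does not end there: the sentence closes with a catch-all, "and other possible cofounders", for which no list, number or selection rule is given.

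The sample size paragraph that follows uses a different procedure: "Power calculations are based on the use of a one-sided, one-sample t-test to evaluate a decrease in Ki67". It claims at least 90% power at alpha 0.05 for a decrease above 0.55 s.d. with 30 patients, and above 1 s.d. in a group of 10.

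Under Secondary objectives, the Mammaprint, ER and PR changes are modelled in the same way, "while adjusting for ki67 in addition to the covariates described above", and "Expected power is the same as for the primary analysis".

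Three design facts bear on this. Section 4, item f: "There is no placebo or non-treatment group". Section 4, item a: "Ten patients will be allocated to each treatment group, for a total of 30 patients". Section 2, primary objective: Ki67 is "measured by IHC as well as single-gene read out", so two read-outs sit under one primary question.

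**The concern.** The plan gives two procedures for one primary question and does not connect them. A one-sample t-test has one obvious target, the mean change. A linear model with drug, ER and PR terms has several coefficients. The plan does not say which coefficient or contrast answers the question, how drug is coded, whether ER and PR are centred, or whether their levels are baseline or surgical values.

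Nor is it clear what the adjustment is for. With every patient treated, there is no treated-versus-untreated comparison from which covariates could remove confounding. They can show which patients change more, but that is a different question.

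At stake is whether the primary p-value has the error rate and power stated for it. Because the covariate list is open, the primary model can also be settled after the data are seen.

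**Working it through.** **Inputs from the plan.** n = 30 in three groups of 10; effect 0.55 s.d. of the change; one-sided alpha 0.05. The plan gives no R-squared for ER and PR and no ER or PR distribution, so those values below are assumptions.

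**1. The plan's own figure.** Power = P(T > t(0.95, df)), with T noncentral t and noncentrality d × √n.
- n = 30: 0.55 × √30 = 3.012; df 29, critical value 1.699; power 0.9025. The stated 90% is reproduced.
- n = 10, 1 s.d.: power 0.8975, which is 90% to rounding.

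**2. Reading A: covariates centred, the three groups averaged.** Least squares with centred covariates and equal groups returns the raw mean as the intercept. In simulated trials the two agreed to about 1e-15. Only the standard error and degrees of freedom change. If the covariates explain nothing:
- treatment only, df 27: 0.9016
- treatment, ER and PR, df 25: 0.9005
- ten model terms, df 19: 0.896

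Power is therefore essentially kept under this reading.

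The standard error is another matter. The model uses about σ√(1−R²)/√n. Over repeated samples of patients, the mean change varies with σ/√n, because the ER and PR values of the sample also vary. The one-sided type I error for the population mean is then approximately P(Z > 1.645 × √(1−R²)):

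| Assumed ER/PR R-squared | 1.645 × √(1−R²) | Closed form | Simulated, adjusted model |
|---|---|---|---|
| 0 | 1.645 | 5.0% | 5.1% |
| 0.05 | 1.603 | 5.4% | 5.4% |
| 0.09 | 1.569 | 5.8% | 5.8% |
| 0.25 | 1.425 | 7.7% | 7.5% |
| 0.49 | 1.175 | 12.0% | 11.6% |

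The simulation used 100,000 trials per row, groups of 10, and two independent standard-normal covariates. The t-test and the treatment-only model stayed at 5.0% to 5.1% throughout.

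**3. Reading B: the software's default intercept.** With reference-group coding, the intercept is the expected change on one drug, at ER = PR = 0 if those terms are uncentred.
- Drug terms only: the intercept is the mean of 10 patients. Noncentrality 0.55 × √10 = 1.739, df 27, critical value 1.703; power 0.52.
- Uncentred ER and PR with no effect on change, 20,000 simulated trials each: about 10% power if ER has mean 85 (SD 15) and PR mean 60 (SD 30); about 17% if ER has mean 70 (SD 25) and PR mean 50 (SD 30). The intercept's SD was 1.43 and 0.79, against 0.18 for the raw mean.
- If ER or PR does predict change, this intercept is no longer the mean change: in two assumed settings it averaged −1.55 where the mean was 0.52, and 1.39 where the mean was 0.57.

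**4. Secondary ER and PR outcomes.** If the covariate is the baseline level, it forms part of the outcome. With equal SDs and baseline-surgery correlation r, Var(change) = 2σ²(1−r) and Cov(baseline, change) = σ²(1−r), so baseline alone gives R² = (1−r)/2. At assumed r of 0.8, 0.5 and 0.2, R² is 0.10, 0.25 and 0.40, and the simulated type I error of the adjusted model is 6.0%, 7.6% and 10.0%. The t-test stays at 5.0% to 5.1%.

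**5. The open covariate list.** Under reading A, taking the most favourable subset of 2 or 4 optional pure-noise covariates gave a one-sided error of about 5.3% and 5.7%.

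**The case against.** Sizing on a simple test and analysing with covariates is common and not in itself an error. On reading A it costs almost nothing: 0.9025 against 0.9005. The model standard error is valid conditional on the ER and PR values observed, so inflation arises only if the target is the mean change in a wider population, which the plan does not state. All patients are ER+ and PR+, so a low R-squared for Ki67 change may be more likely, and at 0.05 or below the inflation is negligible. Choosing among noise covariates adds little. All of this stands and limits the severity.

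It does not remove the point. Each of these defences relies on a centred, group-averaged contrast that the plan does not specify.

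Four stronger readings are tempting, and the documents do not support them:
- A reader might infer that adjustment can never alter the estimate. That holds only with centring at the sample means and equal groups; reading B gives a different quantity.
- A reader might infer that the stated power is wrong or the trial too small. The figure is right for the test it names, and it falls only under reading B, which the plan neither adopts nor excludes.
- A reader might infer that the type I error is known to be inflated. The size depends on an assumed R-squared and on the choice of target.
- A reader might infer that the side of the test is undefined. The aim of showing a reduction, with the sample size paragraph, fairly implies one-sided.

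**Conclusion.** The point holds, with modest severity; it should be fixed before analysis. The primary model is not the test for which alpha and power are stated, and its tested contrast, coding, ER/PR time point and full covariate list are undefined. The consequence depends on what is done. A centred, averaged contrast keeps about 90% power, but its standard error can be too small for the population mean change. A default intercept tests something else and does not deliver the stated power.

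The 52% figure follows from the plan's own sample size and effect. The 10% to 17% range rests on assumed ER and PR distributions, and the inflation figures on assumed R-squared values and a population-mean target. The secondary ER and PR figures further assume that baseline level is meant, that SDs are equal, and that the other covariates are independent of the baseline level.

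**What to change.** State the primary test as a one-sided, one-sample t-test at alpha 0.05 that mean (baseline minus surgery) %Ki67 by IHC exceeds 0 in all participants. The sample size already assumes this test. If treatment is to stay in the primary analysis, test instead the mean change averaged over the three treatment groups, with treatment as the only covariate, one-sided at 0.05. Choose one of the two in advance.

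Keep the ER/PR-adjusted model as a secondary analysis of factors associated with the size of the change, using baseline ER and PR, mean-centred, with no other covariates chosen after the data are seen. Use the same unadjusted test of mean change for the Mammaprint, ER and PR outcomes. Call the single-gene Ki67 read-out supportive, so that one test decides the primary question.

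The cost is protocol wording only, with no extra patients or data. Any apparent precision gain from ER/PR adjustment is given up. The plain t-test is also somewhat conservative if the drugs differ: type I error 4.2%, 2.9% and 1.0% when treatment group explains an assumed 0.09, 0.25 and 0.49 of the variance, with power at 0.55 s.d. still 0.91, 0.93 and 0.96. In the same settings the treatment-only alternative avoids this, with type I error 4.9% to 5.0% and power 0.92, 0.96 and 0.99.
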